1 LIST OF ABBREVIATIONS

ADE	Adverse Device Effect
AE	Adverse Event
AP	Anterior-Posterior
BS	ENBritish Standard European Norm
21 CFR	Code of Federal Regulation: Title 21
CE	Conformité Européenne
CIP	Clinical Investigational Plan
CR	Cruciate Retaining
CRF	Case Report Form (paper)
DVT	Deep Vein Thrombosis
EC	Ethics Committee
eCRF	Electronic Case Report Form
EMEA	Europe/Middle East/ Asia-Pacific
EU	European Union
FB	Fixed Bearing
FDA	Food and Drug Administration
GCP	Good Clinical Practice
HTO	High Tibial Osteotomy
ICD	Informed Consent Document
IRB	Institutional Review Board
ISO	International Organization for Standardization
IRR	Independent Radiographic Reviewer
ITT	Intent To Treat
MEDDEV	Medical Device Guidance Document(s)
NIDJD	Non-inflammatory Degenerative Joint Disease
OR	Operating Room
PHI	Personal Health Information
PI	Principal Investigator
PMCF	Post-Market Clinical Follow-up
Post-op	Post-operative
PP	Per Protocol Analysis

Pre-op	Pre-operative
RUI	Reusable Instruments
SADE	Serious Adverse Device Effect
SAE	Serious Adverse Event
SAS®	Statistical Analysis System
SUI	Single Use Instruments
TKA	Total Knee Arthroplasty
UADE	Unanticipated Adverse Device Effect
UK	United Kingdom
US	United States
USADE	Unanticipated Serious Adverse Device Effect
UTO	Upper Tibial Osteotomy (See also HTO)

2 SUMMARY

TITLE:	Comparison of Alignment achieved using Single-Use versus Reusable Instrumentation in Total Knee Arthroplasty (TKA): A Prospective, Non-Randomized Multi-Center Investigation.
Short Title:	SUI vs. RUI
Protocol Number:	10002
Treatment Device:	Single Use Instruments (SUI) for implantation of ATTUNE® primary TKA. Four implant configurations are permitted: Cruciate Retaining Fixed Bearing (CR FB), Cruciate Retaining Rotating Platform (CR RP), Posterior Stabilizing Fixed Bearing (PS FB) and Posterior Stabilizing Rotating Platform (PS RP) configurations. Each site will be restricted to using either Cruciate Retaining configurations or Posterior Stabilizing Configurations for both treatment and control groups.
Control Device:	Reusable Instruments (RUI) for implantation of ATTUNE primary TKA. Four implant configurations are permitted: Cruciate Retaining Fixed Bearing (CR FB), Cruciate Retaining Rotating Platform (CR RP), Posterior Stabilizing Fixed Bearing (PS FB) and Posterior Stabilizing Rotating Platform (PS RP) configurations. Each site will be restricted to using either Cruciate Retaining configurations or Posterior Stabilizing Configurations for both treatment and control groups.
Intended Use:	The intended use for the instrumentation and device, applicable to this study, is as follows: Candidates for total knee replacement include patients with severely painful and/or severely disabling Non-inflammatory Degenerative Joint Disease (NIDJD) resulting from osteoarthritis (OA) or post-traumatic arthritis.
Primary Objective:	To determine whether the mechanical axis alignment achieved with SUI instrumentation is non-inferior to the alignment achieved with RUI instrumentation.
Secondary Objectives	
 To compare individual component alignment achieved with SUI vs. RUI of individual components in the frontal and sagittal planes, specifically: distal femoral varus-valgus (FM), proximal tibial varus-valgus (TM), femoral component flexion and tibial slope. To compare the type and frequency of adverse events
Study Design:	Prospective, comparative, sequential, non-randomized, multi-center, controlled study design. Level of evidence: Level III ^A
Number of Sites:	4 Centers Worldwide
Subject Population:	Male and female Subjects who are candidates for primary, total knee arthroplasty between 22 and 80 years of age, inclusive, with noninflammatory degenerative joint disease (NIDJD) resulting from osteoarthritis (OA) or post-traumatic arthritis.
Sample Size:	A total of 88 Subjects will be enrolled in the investigation (44 treatment Subjects and 44 control Subjects).

^A Levels of Evidence for Primary Research Question

TITLE:	Comparison of Alignment achieved using Single-Use versus Reusable Instrumentation in Total Knee Arthroplasty (TKA): A Prospective, Non-Randomized Multi-Center Investigation.
Study Duration:	The estimated duration of this study is 13 months: 8 months for enrollment and 5 months for post-operative follow-up.
Procedure Schedule:	Demographic data will be collected preoperatively. Surgical data will be collected intraoperatively. Post-operatively, radiographic data will be collected at approximately 90 days.
Safety:	All adverse events will be collected from the time of surgery through to the end of the study or the time when that Subject is withdrawn from the study. A listing of expected, procedure-related, early postoperative adverse events (AEs) will be provided and such events will not need to be recorded. The type and frequency of recorded AEs will be analyzed.

2.1 Time and Events Table

Event / Visit	Pre-Op	Surgery	Post-Op
Required Timing (days)	-180d to include day 0	0	30 -150
Discuss Study with Subject	Yes		
Screening Log	Yes		
Informed Consent	Yes		
Enrollment	Yes		
Complete Subject History eCRF	C		
Surgical Procedure 
 Complete Operative Details eCRF Complete Device Log eCRF 		C C	
Radiographs 
 Hip to Ankle Long Film 			R*

 AP View 	R		R

 Lateral View 			R
Complete Adverse Event eCRF		A	A
Complete End of Study/Withdrawal	A	A	C
Advise the Subject when they will next be seen	Yes	Yes	
C= Case Report Form to be completed and submitted in the Electronic data capture system R= Radiograph obtained and submitted R*, For the purposes of this investigation this radiograph will only be performed when the Subject can achieve full leg extension ($\pm 5^\circ$). A= As needed			

3 INTRODUCTION

3.1 Background

Alignment

Successful total knee arthroplasty relies on proper positioning of prosthetic components to restore the mechanical axis of the lower extremity. It is widely accepted that proper alignment is an important factor in the success and longevity of total knee arthroplasties ^[1-4]. Mechanical axis alignment is defined as the line drawn from the center of the femoral head through the center of the knee and ankle. The knee is in proper alignment when these three points are collinear in the frontal plane ^[1]. Many authors have observed that the correct alignment of the lower limb is correlated with clinical success in total knee arthroplasty ^[2-7].

Operating Room (OR) Efficiency

In this era of capitated reimbursement and managed care, cost containment is assuming greater importance in health care. Consequently, operating room efficiency has become higher priority for many institutions ^[8]. As patient volume increases and hospital resources are strained the OR can become a bottleneck in providing efficient, high quality patient care. Optimizing OR performance without compromising safe and high-quality health care for patients is an important goal.

There are a number of studies aimed at increasing operating room efficiency and controlling operating room costs while striving to provide high-quality, technologically advanced surgical services. Often the focus is on streamlining the existing steps that are involved in delivering patient care preoperatively, intraoperatively, and postoperatively ^[10]. This need for improved delivery of care is further critical when one recognizes the increasing number of patients needing TKA. Improved surgical instruments are one factor that may improve OR efficiency and an approach is to introduce Single-Use instruments.

An important aspect of the delivery of surgical care is the time required to prepare the operating room prior to the procedure as well as the turnover time at the conclusion of the surgery. Preparation timeline for every surgical procedure is at risk from various delays. Unwanted delays have occurred related to unavailable sterile instruments, holes found in the sterile wrap of sterilized instruments, the time required to flash sterilize an instrument requested last minute, etc. Prepackaged sterilized Single-Use instruments may help to resolve some of these unwanted delays. Additionally, when single use instruments are combined with preoperative templating to define implant sizing, there should be a substantial reduction in the quantity of instruments brought to the OR (Figure 1). Single use instruments provide a completely clean and sterile instrument for every patient, which is used once and disposed of, removing the need for lengthy decontamination processes^[13].

Figure 3-1: ATTUNE TKA Instrumentation (left to right): Reusable instrumentation; and Single Use instrumentation shown

4 RATIONALE

4.1 Study Rationale

A pre-requisite for SUI adoption is to confirm that the mechanical axis alignment achieved with single use instruments is non-inferior to the alignment achieved with ATTUNE reusable instruments .

4.2 Study Design Rationale

The study was designed as comparative, sequential, non-randomized, multi-center, such that each site has an equal number of Subjects in each treatment group, SUI and RUI. The follow-up period of approximately 90 days was selected due to the time required for most Subjects to be able to achieve full leg extension (within $\pm 5^\circ$), a requirement for obtaining suitable weight-bearing hip-to-ankle radiographs for analysis of alignment. The mechanical axis alignment will be assessed at the 3 month follow-up by independent radiographic review. The sequential design (that is at each site all RUI cases will be completed before doing any of the SUI cases) is set up to ensure that with the control group (RUI), current status of OR efficiency is captured rather than this being influenced by any efficiencies learned from use of the SUI.

4.3 Rationale of Endpoints

Successful total knee arthroplasty relies on proper positioning of prosthetic components to restore the mechanical axis of the lower extremity. It is widely accepted that proper alignment is an important factor in the success and longevity of total knee arthroplasties ^[1-4]. A goal of $0^\circ \pm 3^\circ$ mechanical axis alignment was chosen because the Investigators in this study confirmed they regularly aim for this target.

4.4 Rationale of Study Population

Subjects with NIDJD and determined to be suitable for a cemented, primary TKA with the ATTUNE implant are targeted as this study is on surgical instruments to implant a cemented, primary ATTUNE implant. Narrowing the indications to exclude inflammatory arthritis was done to have more homogeneity in the population, including bone quality that could possibly influence bone resections with the two instrument types.

5 SUBJECT DEFINITION

Male and female Subjects, aged 22-80 years, inclusive, with Non-Inflammatory Degenerative Joint Disease (NIDJD) resulting from osteoarthritis (OA) or post-traumatic arthritis and suitable candidates for primary, total knee arthroplasty using an ATTUNE system are eligible for enrollment in this study.

Subjects who do not meet all of the inclusion criteria or meet any of the exclusion criteria are automatically excluded from study consideration and participation. Subjects, who meet all entry criteria and are properly consented, may be excluded from participation because of:

- Surgeon preference/medical opinion (under very limited conditions not to introduce Investigator bias).
- Withdrawal of consent from study participation.

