8.2.1 Subject Screening

All Patients who present with NIDJD affecting the knee, and are candidates for primary, cemented TKA, and who generally meet the study requirements, will be screened for eligibility and will be listed on the Screening and Enrollment Log in order to document that the Subject selection was unbiased. The date of screening, the results of screening (included or not) and the primary reason for not including the patient (*e.g.*, does not satisfy eligibility criteria, not interested in participating) will be recorded on this log. The original log is to be retained at the Site and a copy sent to the Sponsor regularly during enrollment. A flowchart demonstrating the screening process and definition of enrollment is illustrated in Figure 8-1.

Eligible Patients who agree to participate in the study will be required to sign an Informed Consent Document prior to any study related procedures being done. ***After signing the Informed Consent, study Subjects are defined as "enrolled" and site will complete the non-standard of care pre-operative data collection.***

It is expected that complete data collection will be obtained for all enrolled Subjects, with the only exception being a Subject who is subsequently withdrawn. See Section 8.4 Discontinuation of Subject Participation (Withdrawal) for details.

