8.3.6 Management of Bias

To avoid potential bias and ensure consistency, an Independent Radiographic Reviewer (IRR) will be used to evaluate the post-op 90 day radiographs. This is an open investigation by design. Only the independent radiographic reviewer will be blinded regarding the instrumentation. The X-ray images will be provided with all Subject PHI information removed prior to assessment by the IRR. Data from the IRR radiographic evaluations (not the Investigators) will be used for determination of radiographic success criteria. Details of the radiographic assessment and means of submitting radiographs for review are detailed in Exhibit F, the Radiographic Protocol.

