8.4.3 Enrollment Replacement Rules

Since Subjects are enrolled at the time of consent, any Subject that is withdrawn preoperatively or intraoperatively prior to receiving the study implant will be replaced with subsequent Subjects. Overall, the number of Subjects who received an ATTUNE implant using a study device (with either the RUI or SUI instrumentation), across all sites must meet the sample size of 88.

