10.2 Treatment Assignment

See Section 7.

Randomization will not be employed in this study. Each site will consecutively enroll all RUI cases prior to enrolling consecutive SUI cases.

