## 8.2 Disposition of Study Subjects

An overall summary of the number of subjects who were (or had): Enrolled, Enrolled but not treated, in the Safety Analysis Set, in the Per Protocol Set, withdrew before study completion, and who completed the study will be tabulated for all sites combined. A listing will be created for completion status and will include columns for all of the items included in the summary table.

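### Protocol section 5 lets an unblinded surgeon drop and replace an eligible, consented subject on undefined grounds, which permits arm-dependent selection and does not match section 8.4.1

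*Protocol*

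**What the plan says.** Protocol section 5 first sets the entry criteria as a filter and then adds a further exit: "Subjects, who meet all entry criteria and are properly consented, may be excluded from participation because of" one of two reasons. The second is withdrawal of consent. The first is "Surgeon preference/medical opinion (under very limited conditions not to introduce Investigator bias". Neither document says what the limited conditions are.

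The surrounding provisions are:

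- **Replacement (Protocol 8.4.3):** "any Subject that is withdrawn preoperatively or intraoperatively prior to receiving the study implant will be replaced with subsequent Subjects".
- **Order of cases (Protocol 10.2):** "Each site will consecutively enroll all RUI cases prior to enrolling consecutive SUI cases".
- **Enrolment (Protocol 5.3 and 8.4.3):** "Since Subjects are enrolled at the time of consent".
- **Blinding (Protocol 8.3.6):** "Only the independent radiographic reviewer will be blinded regarding the instrumentation". Under section 7, one surgeon per site does all cases in both phases.
- **Pre-operative removal (Protocol 8.4.1 and Table 8-5):** the investigator may withdraw a subject for safety or eligibility reasons, and the subject may withdraw consent. Surgeon preference does not appear.
- **Reporting (SAP 8.2):** counts, including subjects enrolled but not treated, "will be tabulated for all sites combined", plus a listing of completion status.

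**The concern.** The trial is open, sequential and non-randomised, and its primary analysis is an unadjusted t-test on the Per Protocol set. Comparability of the arms therefore depends heavily on which knees reach surgery in each phase. Section 5 gives the person who knows the phase a discretion over subjects already judged eligible, and the replacement rule fills the gap with another knee.

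If knees expected to align poorly were dropped more often in the SUI phase, the SUI mean absolute angle would fall and the comparison would lean towards non-inferiority. The planned analyses would not correct this:

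- A dropped subject has no study radiograph, so the Safety Set sensitivity analysis in SAP 8.7 cannot bring that knee back.
- The baseline list in SAP 8.3 contains no measure of deformity or pre-operative alignment.
- Protocol section 6 (footnote D) says pre-operative plans are not collected.

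**Working it through.** **Text check.** Three provisions bear on an eligible, consented subject before surgery.

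1. Section 5 permits exclusion for surgeon preference or medical opinion.
2. Section 8.4.1 and Table 8-5 describe only safety, ineligibility and withdrawn consent. The section 5 exit has no matching category there.
3. Section 10.2 requires consecutive enrolment. Enrolment is consent, so a subject dropped afterwards was still enrolled in sequence. What is lost is the consecutiveness of the subjects operated on and analysed.

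**The plan's own figure.** Inputs from Protocol 10.9 and SAP 7: margin 1.5°, SD 1.87°, one-sided alpha 0.05, 1:1 allocation, true difference 0. Exact noncentral-t power is 94.8% at 34 per group and 95.3% at 35, so the stated 35 reproduces. Allowing 20% loss, 35/(1 − 0.20) = 43.75, rounded up to 44. The discretion changes none of these figures, because excluded subjects are replaced.

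**Illustrative size of a selection effect.** The documents give no exclusion rate and no measure of how well a surgeon can forecast alignment. Both are assumptions here. All exclusions are placed in the SUI arm, and the true difference is set at exactly 1.5°, where the error rate should be 5%.

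Standard error: 1.87 × √(2/35) = 0.447° with 35 evaluable per arm; 1.87 × √(2/44) = 0.399° with 44.

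*Model A, imperfect forecast.* The k subjects with the worst forecast among 44 + k candidates are dropped. Let x = k/(44 + k), z the upper-x normal point, φ the normal density, and ρ the correlation between forecast and outcome. Then shift = ρ × 1.87 × φ(z)/(1 − x), and the error comes from the noncentral t with noncentrality shift/SE. For k = 4 and ρ = 0.5: x = 0.083, φ(z) = 0.153, shift = 0.5 × 1.87 × 0.153/0.917 = 0.156°.

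*Model B, fixed gap.* Each dropped knee would have been g degrees worse than its replacement. Shift = k × g/44, and error = 1 − Φ(1.645 − shift/0.399). For k = 4 and g = 2.5: shift = 10/44 = 0.227°, error = 1 − Φ(1.075) = 14.1%.

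| SUI exclusions | Assumption | Shift favouring SUI | Error, 35 per arm | Error, 44 per arm |
|---|---|---|---|---|
| 2 | A, ρ 0.1 to 0.5 | 0.02° to 0.09° | 5.4% to 7.4% | 5.5% to 7.8% |
| 4 | A, ρ 0.1 to 0.5 | 0.03° to 0.16° | 5.8% to 9.7% | 5.9% to 10.5% |
| 2 | B, g = 2.5° | 0.11° | – | 8.7% |
| 4 | B, g = 2.5° | 0.23° | – | 14.1% |
| 4 | B, g = 2° to 3° | 0.18° to 0.27° | – | 11.7% to 16.8% |

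The two models can be compared. Under A with a perfect forecast, the worst 4 of 48 lie 1.87 × 0.153/0.083 ≈ 3.4° above the mean. A gap of 2.5° therefore implies ρ of about 2.5/3.4 ≈ 0.7, which is strong forecasting among knees already screened for severe deformity.

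If the discretion is used equally in both arms, the shifts cancel in the difference and the error stays at about 5%.

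**The case against.** The other side has a good deal to say, and most of it limits the point without removing it.

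- **A reader might infer that section 5 contradicts consecutive enrolment.** It does not, because enrolment is consent.
- **A reader might infer that consecutive cases are the only protection.** They are not. Alignment is read by an independent reviewer blinded to instrumentation, one surgeon does both arms at each site, and inclusion criterion (d) requires suitability for either instrument set. These stand, but a blinded reading does not undo selection made before surgery.
- **A reader might infer that an excess of exits in one phase would be invisible.** Protocol 8.4 requires an End of Study/Withdrawal eCRF for every discontinuation after consent, and 12.4 requires the date and reason. Subject numbers carry site and sequence, and SAP 8.2 adds a completion listing. An excess could be traced. What is missing is any stated summary by phase and reason. The table shells are a separate document that was not available.
- **A reader might infer that the screening log misses these subjects.** It covers patients "and who generally meet the study requirements, will be screened for eligibility and will be listed on the Screening and Enrollment Log", and anyone who met all criteria and consented is among them.
- **The bullet also names medical opinion and states a limit.** True, so it is not purely non-medical discretion. The limit is an aim, however, with no rule behind it.
- **Table 8-5 is presented as examples.** This weakens the argument from a missing row, but the text of 8.4.1 is narrower than section 5 as well.
- **Deleting the bullet would not end discretion.** This stands. Section 8.2.2 places the eligibility assessment after consent, and several criteria rest on the investigator's opinion, including exclusion (a) on severe deformity.

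**Conclusion.** The point holds as an avoidable weakness in the protocol text: an undefined discretion after consent, followed by replacement, exercised by someone who knows the arm, and not matched by the section on pre-operative withdrawal. It permits arm-dependent selection. Nothing in the documents shows that selection will occur.

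The size is unknown. For 2 to 4 exclusions confined to SUI, the one-sided error at the margin is about 5% to 10% with forecast correlations of 0.1 to 0.5. It reaches about 14% for 4 exclusions under a 2.5° gap, which has no source in the documents. With equal use in both arms it stays at about 5%. These figures assume that SUI is truly 1.5° worse and that every exclusion favours SUI. A reader might take 14% as the expected error rate, but the documents do not support that.

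A change is worthwhile because it is specific and cheap.

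**What to change.** 1. In Protocol section 5, delete surgeon preference as a ground for excluding an eligible, consented subject. Keep only a medical or safety reason, recorded on the Screening and Enrollment Log before surgery.
2. Reconcile section 5 with section 8.4.1 and Table 8-5 so that all three give the same grounds, and add the retained ground to the table.
3. In SAP 8.2, report all consented subjects not operated on, and their replacements, by site, instrument phase and reason.

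The cost is a sentence of protocol text, a table row and one further split of a disposition table, using data the eCRF and log already collect. The downside is slightly less surgeon discretion after consent. Opinion-based eligibility criteria would still be assessed after consent, so some room for selection would remain; the report by phase would help to show whether it was used unevenly.

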5.1 Inclusion Criteria

Subjects meeting **all** of the following specific criteria will be considered for participation in the study:

- a) Subjects with severely painful and/or severely disabling Non-inflammatory Degenerative Joint Disease (NIDJD) resulting from osteoarthritis (OA) or post-traumatic arthritis.
- b) Subject is male or female and between the ages of 22 and 80 years old, inclusive.
- c) Subject requires a primary total knee replacement and is considered by the Investigator to be suitable for the specific knee prosthesis identified in the protocol.
- d) Subject, who, in the opinion of the Investigator, is suitable for implantation using either RUI or SUI instrumentation.
- e) Subject is able to speak and read English to facilitate comprehension of the Informed Consent Document.
- f) Subject has given voluntary, written informed consent to participate in this clinical investigation and has authorized the transfer of his/her information to DePuy Synthes Joint Reconstruction.
- g) Subject, in the opinion of the Investigator, is able to understand this clinical investigation and is willing and able to perform all study procedures and follow-up visits and co-operate with investigational procedures.

